During the first 8-week trial, patients will be seen at weeks 0, 1, 2, 3, 4, 6 and 8 for clinical assessment and mood ratings. During the continuation trial, they will be seen at weeks 8, 10, 12, 14 and 16. The main outcome measure for the study will be the scores on the Montgomery-Asberg Depression Rating Scale, MADRAS [62]. All patients will also be assessed with the Young Mania Rating Scale, YMRS [63], the Clinical Global Impression-Bipolar version, CGI-BP [64], and the UKU side-effects scale [65]. In all visits, patients will be seen by the study psychiatrist and the research staff will complete mood ratings with the MADRAS, YMRS, CGI-BD, and the UKU side-effects scale.

At baseline (before randomization), week 8 and week 16 blood will be sampled for proinflammatory markers (C-reactive protein, soluble interleukin (IL)-2 receptor, IL-6 and tumor necrosis factor (TNF)-alpha), and oxidative stress

markers (superoxide dismutase activity and catalase activity, serum thiobarbituric acid reactive substances (TBARS)), which have been reported to be elevated in BD patients [34] [33] [35]. These blood samples will be stored for possible future research on biomarkers or future genetic studies for up to 20 years, for use in pharmacogenetic research during this 20 year timeframe. The samples will be stored at the Wet Lab, in a double locked -80 degrees freezer, at [REDACTED]

[REDACTED] for future use studying factors of Bipolar Disorder. When (or before) the 20 year period ends, the blood sample will be destroyed.

Patients will complete neuropsychological testing at baseline and Week 16. The testing will include CANTAB, WASI, and WRAT assessments and will take approximately 3-4 hours.

At the screening visit, week 8, and week 16 we will also be testing the Lithium levels in all patients that have been prescribed and currently taking the medication for study purposes. This extra test will be conducted for the safety of the patient and more Lithium level tests can be ordered under the PI's discretion throughout the 16 week trial.

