### **General Data Analytic Strategies**

All statistical analyses will use SAS v. 9.2 (SAS Institute Inc., Cary, N.C.). Preliminary data analyses inspecting group differences on demographic and baseline variables will evaluate posterior distributions for differences in proportions and means, as well as for correlations between baseline variables and specified outcomes. Baseline or demographic variables for which the posterior distribution indicates there is > 99% chance of a difference across groups, and for which there is a > 99% chance of a non-zero correlation with outcomes, will be defined as potential confounders and will result in two sets of analyses: one in which the relevant variable is included as a covariate and one in which it is not. This will permit determination of the degree to which any group differences might confound conclusions regarding treatment.

Evaluation of the primary outcome, proportion of patients demonstrating > 50% decrease in depression scores on the MADRS, as a function of treatment will use a beta-binomial model and contingency tables with chi-square testing for Bayesian and Frequentist approaches respectively. Additional analyses will use the generalized linear modeling. Count, dichotomous and continuous Bayesian analyses will be conducted using Poisson (Proc GENMOD; SAS 9.2), logistic (Proc GENMOD; SAS 9.2), linear (Proc GENMOD; SAS 9.2) regression respectively. Distributional assumptions will be evaluated via inspection of residual plots and, where possible, by formal statistical tests. Violation of assumptions will be addressed, depending upon statistical technique, through the use of transformations, robust methods, and stratification.

Unless otherwise indicated in the data analytic plan, priors will be specified as neutral and diffuse. The beta-binomial model will use a  $\sim\text{Beta}(1,1)$  prior distribution. For linear, Poisson, and logistic regression, priors will take the form  $\sim\text{N}(0, 1 \times 10^6)$  in the linear, log, and log(odds) scales respectively. Convergence of Bayesian analyses on the posterior distributions via Monte-Carlo Markov chain (MCMC) will be assessed via graphical (Trace Plot, Autocorrelation Plot) and quantitative (Geweke Diagnostics, Gelman-Rubin Diagnostics, and Heidelberger-Welsh Diagnostics) evidence. Evaluation of posterior distributions will permit statements regarding the probability that effects of varying magnitudes exist, given the data.

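### For the additional continuous analyses of MADRS and YMRS, the plan names only linear regression, although both scales are rated at six post-baseline visits up to week 8

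*Combined protocol and SAP*

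**What the plan says.** Study procedures sets the schedule: "patients will be seen at weeks 0, 1, 2, 3, 4, 6 and 8 for clinical assessment and mood ratings". That is one baseline and six post-baseline visits. In the continuation stage "they will be seen at weeks 8, 10, 12, 14 and 16", which adds four more. At all visits "research staff will complete mood ratings with the MADRAS, YMRS, CGI-BD, and the UKU side-effects scale". The same section states that "The main outcome measure for the study will be the scores on the Montgomery-Asberg Depression Rating Scale".

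General Data Analytic Strategies defines the primary outcome differently, as the proportion of responders on the MADRS, tested with a beta-binomial model and chi-square. It then says "Additional analyses will use the generalized linear modeling", and assigns continuous outcomes to "linear (Proc GENMOD; SAS 9.2) regression respectively". On priors it says "For linear, Poisson, and logistic regression, priors will take the form" of a diffuse normal; it gives no prior for a within-patient covariance or a random effect. Violated assumptions are to be handled "through the use of transformations, robust methods, and stratification".

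The only dropout rule, in the same section, counts dropouts as non-responders. The mediation models described there also have no stated repeated-measures structure.

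**The concern.** Repeated ratings on one patient are correlated. A linear regression with no stated visit and no within-patient covariance can be run in two ways, and the plan does not choose between them.

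- **One value per patient at week 8.** The error bars are sound with complete data. Five of the six post-baseline ratings go unused, as do all ratings from patients who leave before week 8. Study procedures ends participation for patients who worsen markedly or become acutely suicidal, so dropout may well follow earlier scores. A regression of completers adjusted only for baseline is then biased in general.
- **All six visits as separate rows.** The ratings are treated as independent, the standard errors are too small, and the false-positive rate rises. A Bayesian version has the same fault, because its likelihood would assume independence and its intervals would be too narrow.

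The non-responder rule cannot be applied to a score, so missing continuous data have no stated treatment under either reading.

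**Working it through.** **The plan's own figure.** The documents give no standard deviation, effect size or power for a continuous MADRS analysis. The stated power is for the binary outcome: 81.80% for 0.25 versus 0.50 with 60 per group. With pooled variance and a two-sided 0.05 test, Φ[(0.25 − 1.96·√(2·0.375·0.625/60)) / √((0.25·0.75 + 0.50·0.50)/60)] = Φ(0.0768/0.0854) = 81.6%. It reproduces and does not depend on the continuous analysis.

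**Inputs.** Six post-baseline visits (weeks 1, 2, 3, 4, 6, 8) come from Study procedures. Within-patient correlation ρ and dropout d are not in the documents, so all values below are assumptions.

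**Reading 1, week 8 only: error rate.** In 4,000 simulated null trials per setting (40 or 60 per arm, ρ 0.3-0.7 exchangeable, or 0.9 per week serial), the baseline-adjusted week-8 regression rejected 4.3-5.5% of the time. The error bars are right with complete data.

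**Reading 1: precision.** Let Σ be the 6×6 covariance of the visits after baseline adjustment.
- Completer regression: variance ∝ Σ₆₆/(1 − d).
- Mixed model: variance ∝ the week-8 element of (Σₖ pₖ Iₖ)⁻¹. Here Iₖ is the inverse covariance of the first k visits padded with zeros, p₆ = 1 − d, and p₁ to p₅ = d/5 each.

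Reduction in week-8 variance with baseline in both models:

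| ρ | d | Exchangeable | Autoregressive per visit | Autoregressive per week |
|---|---|---|---|---|
| 0.5 | 20% | 3.9% | 1.5% | 0.3% |
| 0.5 | 30% | 5.9% | 2.5% | 0.5% |
| 0.7 | 20% | 5.4% | 3.9% | 1.5% |
| 0.7 | 30% | 8.2% | 6.3% | 2.5% |

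With baseline left out of both models, the exchangeable range would be 7-18%. That does not describe the model recommended here, which includes baseline.

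**Reading 1: bias.** In one illustrative simulation with dropout driven by the week-4 score, week-8 completer regression shrank the treatment effect by about 7%. A check used a week-8 effect of 0.5 SD, exchangeable ρ 0.5-0.7, dropout 20-30%, and log-odds of dropout rising by 1 to 2 per SD of the week-4 score. Shrinkage was about 1-4% if half the effect is present at week 4, and about 3-8% if all of it is. An estimate that also used the week-4 score recovered the true effect to within about 0.5%.

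**Reading 2, six visits as independent rows.** Without baseline, the design effect is 1 + 5ρ, the true standard error is √(1 + 5ρ) times the reported one, and the actual error rate is 2·[1 − Φ(1.96/√(1 + 5ρ))]. With baseline in the model, the residual correlation is (ρ − ρ²)/(1 − ρ²) = ρ/(1 + ρ), which replaces ρ.

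| ρ | SE ratio, no baseline | Error rate, no baseline | Error rate, with baseline (formula) | Error rate, with baseline (simulated) |
|---|---|---|---|---|
| 0.3 | 1.58 | 21.5% | 18.2% | 17-19% |
| 0.5 | 1.87 | 29.5% | 23.0% | 24% |
| 0.7 | 2.12 | 35.6% | 26.2% | 26% |

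Under serial correlation of 0.9 per week, the simulated baseline-adjusted rate is about 29%. The overall range is about 17-36%.

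**The case against.** The strongest reply is that little hangs on this. The primary test, the interim pruning rule and every power figure use binary response, one value per patient. The criticised sentence covers additional analyses. That is correct. A reader might infer from the Study procedures wording on the main outcome measure that the primary test is at fault, but General Data Analytic Strategies defines the primary outcome as binary. The conflict between the two sections is a separate matter.

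Second, a reader might infer that the plan will produce false-positive rates of 17-36%. The documents do not support that. No section says visits will be stacked, and one value per patient is the more natural reading, since it matches the binary endpoint. Those figures show only what the silence permits. The general mention of robust methods does not close the gap, because it does not name clustering by patient.

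Third, the choice is not strictly between wasting visits and wrong errors. Regression on a pre-specified patient-level mean or slope would use the visits with valid errors. This stands, but no such summary is specified. For a time-averaged effect, the baseline-adjusted mean of six visits would have 0.36-0.51 of the variance of one visit (ρ 0.3-0.7). That is a different target from the week-8 difference and should not be read as the gain available there.

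Fourth, the plan invokes intention to treat, so completer analysis is an inference. That is fair, but the only operational dropout rule is binary. Finally, a mixed model removes dropout bias only if data are missing at random. Removal for acute worsening may reflect a state that earlier scores did not capture. This also stands.

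**Conclusion.** The point holds for the additional continuous analyses of MADRS and YMRS, and only for those. The named method neither uses nor accounts for the repeated ratings, and the plan fixes no visit, correlation structure or missing-data rule for a continuous score.

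Under the natural week-8 reading, the standard errors are valid with complete data. The precision lost is modest: about 4-8% of variance if exchangeable and 0-6% if autoregressive, assuming ρ 0.5-0.7, dropout 20-30% and baseline adjustment. Bias from dropout related to earlier scores is the better reason to change. Its size cannot be known from the documents; the illustrative settings gave shrinkage of roughly 1-8%. The inflation to roughly 17-36% (assumed ρ 0.3-0.7, with or without baseline) applies only if visits are stacked, which the plan neither states nor excludes. The change is worth making because it is cheap and uses data already collected.

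**What to change.** In General Data Analytic Strategies, replace linear regression for MADRS and YMRS with a mixed model for repeated measures over weeks 1-8. Include baseline score, visit, treatment and treatment-by-visit terms, with unstructured within-patient covariance (6·7/2 = 21 parameters for six visits). Report the week-8 treatment difference. Use the same likelihood in the Bayesian version, and state a prior for the covariance, which the plan does not now give. Say explicitly that repeated ratings will not be entered as independent rows.

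Restrict the model to weeks 1-8. Study Design and Study procedures re-randomise non-responders at week 8, so later ratings cannot simply be pooled with the first six.

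The cost is a few sentences in the plan and modest programming, possibly with a procedure other than Proc GENMOD. No new visits, patients or data are needed. The drawback is reliance on missing at random, which the plan should state and probe with a sensitivity analysis.

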### **Statistical analyses:**

#### Simulation Study

In preparation of this application we conducted a Monte Carlo simulation study to assess the relative merits of the proposed DTL adaptive design over a non-adaptive, parallel-group approach. Specifically, the goal of this study was to demonstrate that the DTL design would result in the maximum number of subjects being treated in the most promising conditions, i.e., appropriate "pruning" of less effective conditions. Simulation scenarios including one that posits no effect across conditions and others, assuming specific anticipated effects, permits evaluation of Type I and Type II Error rates respectively. Sample size for each simulated trial was set at  $n = 160$ . Response to treatment was defined, dichotomously, as  $> 50\%$  decrease in depression score as measured on the MADRS. Specification of effects for the simulations assumed that the rate of response in the placebo condition is 25%, while 1000 mg aspirin qd and 1000 mg NAC bid have comparable effects with response rates of 50% each. The combination of 1000 mg aspirin qd and 1000 mg NAC bid is anticipated to demonstrate an additive effect yielding a 70% response rate. At 50% information gathering, defined as  $n = 80$  subjects having completed the study, a Bayesian interim analysis determined the posterior probability that treatment conferred benefit. Benefit was defined as the absolute difference in response rate for each treatment relative to placebo. The remaining 80 subjects were allocated to the retained (non-pruned) treatments, with the probability of assignment to any given group based on the number of groups continuing in the study.

Pruning/Retention Rules. Simulation scenarios considered a variety of pruning rules that varied in stringency for 1) detecting a clinically decisive difference ( $>10\%$  from placebo), and 2) selecting the best performing treatment. All simulations assumed a  $\sim\text{Beta}(1,1)$  prior distribution for the probability of treatment response in all study conditions. A  $\text{Beta}(1,1)$  prior models values within the range  $[0,1]$  in which all values have the same probability of occurring. This constitutes a vague, neutral prior distribution which reflects uncertainty preceding data accrual. At 50% of data gathering ( $n = 80$ ) the prior (i.e.  $\sim\text{Beta}(1,1)$ ) was updated with data generated from a binomial distribution for each

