If  $N = 160$  participants are randomized across four conditions in a 1:1:1:1 ratio, contrasts for treatment response rates versus placebo will use  $n = 40$  participants per cell. For Scenario 1, assuming  $n = 40$  per group and  $\alpha = 0.05$ , power to detect the difference between the proportions 0.25 and 0.50 is 65%. Using the same assumptions power to detect the difference between the proportions 0.25 and 0.70 is >99%. For Scenario 2, assuming  $n = 40$  per group and  $\alpha = 0.05$ , power to detect the difference between 0.25 and 0.5 is 65%. More generally, for comparison of two independent proportions, sample sizes of  $n = 40$  per group and  $\alpha = 0.05$  provide 80% power to detect a difference between 0.25 and 0.55. Such a sample is underpowered for two of the effects in Scenario 1, and all of the effects in Scenario 2. Recall, however that the proposed Bayesian adaptive design results in altered cell sizes such that the most promising treatment and placebo each receive an average of  $n = 60$  participants. (This is substantiated by the simulation results). Assuming  $n = 60$  participants per group and  $\alpha = 0.05$ , power to detect the difference between 0.25 and 0.50 is 81.80%, while power to detect the difference between 0.25 and 0.70 is > 99%. More generally, a sample of this size provide 80% power to detect the difference between 0.25 and 0.49 with  $\alpha = 0.05$ .

In summary, a Bayesian adaptive approach demonstrates adequate operating characteristics (Type I and II Error Rates) for the current trial. The method results in allocation of more participants to the most effective condition. Finally, the approach permits frequent analyses with more desirable Type I and Type II Error rates.

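### The N(0, 1×10^6) prior on the log-odds and log scales decides the answer when exactly one of two compared arms has no events; a minor point, confined to sparse additional outcomes

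*Combined protocol and SAP*

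**What the plan says.** All of the relevant wording is in General Data Analytic Strategies.

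- General stance on priors: "Unless otherwise indicated in the data analytic plan, priors will be specified as neutral and diffuse".
- Primary responder outcome: "The beta-binomial model will use a" Beta(1,1) prior. The Simulation Study section uses the same prior for the pruning rule.
- Regression models: "For linear, Poisson, and logistic regression, priors will take the form" N(0, 1×10^6), applied "in the linear, log, and log(odds) scales respectively". The text does not say whether 1×10^6 is a variance or a standard deviation.
- Where these models are used: "Count, dichotomous and continuous Bayesian analyses will be conducted using Poisson (Proc GENMOD; SAS 9.2), logistic (Proc GENMOD; SAS 9.2), linear" regression. They are additional to the primary analysis.
- How results will be read: "Evaluation of posterior distributions will permit statements regarding the probability that effects of varying magnitudes exist, given the data".

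The plan lists MCMC convergence checks. It gives no rule for empty cells and no prior-sensitivity analysis.

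**The concern.** A normal prior with a very large variance is harmless on a linear scale but not on a log-odds or log scale. There it places almost all of its weight on event rates indistinguishable from 0 or 1, and on odds or rate ratios of no clinical meaning. Data normally overwhelm it. An empty arm is the exception: its likelihood stays flat as the log-odds or log-rate falls towards minus infinity, so nothing in the data stops the posterior from following the prior outwards.

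The plan intends to make direct probability statements from these posteriors. In a sparse table such a statement could report near-certainty of a difference that the counts hardly support. It would also conflict with the Beta(1,1) model that the same section describes as neutral.

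**Working it through.** **Inputs from the plan.** The prior is N(0, 1×10^6), read here as a variance (SD 1000). For arm sizes, "participants are randomized across four conditions in a 1:1:1:1 ratio" and the interim is at 80, so 80/4 = 20 per arm. Then "The remaining 80 subjects were allocated to the retained (non-pruned) treatments". With one active arm and placebo retained, each reaches 20 + 80/2 = 60, which reproduces the plan's stated average of 60, and each pruned arm stays at 20 by first randomisation. As a check that the set-up is understood, power for 0.25 versus 0.50 at 60 per arm comes to 81.6% (plan: 81.80%). The plan gives no figure for how the normal prior behaves.

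**Assumed.** The tables 0/20 versus 1/60 and 0/20 versus 3/60, and event rates of 5% and 10%.

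**1. What the prior implies.** A rate between 1% and 99% means |log-odds| < ln 99 = 4.595. Prior mass there is 2Φ(4.595/1000) − 1 = 0.37%. Beta(1,1) puts 98% there.

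**2. Posterior with one empty arm.** The model is a (log-odds or log-rate in the 60-patient arm) and a + b (in the 20-patient arm), each coefficient with SD 1000. With no events in the second arm:

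- For b < 0 the likelihood is nearly flat, so the weight is about half the normal curve: 1000 × √(π/2) = 1253.
- For b > 0 the likelihood cuts off quickly. With k events among 60, and using the Poisson form, the weight is m = ∫ from 1 to ∞ of (1/t) × [3/(3+t)]^k dt, where 3 = 60/20.
- k = 1: m = ln 4 = 1.386. P(ratio < 1) ≈ 1 − 1.386/1253 = 99.89%.
- k = 3: m = ln 4 − 3/4 − 9/32 = 0.355. P(ratio < 1) ≈ 1 − 0.355/1253 = 99.97%.

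Full numerical integration of the logistic model gives the same 99.89% and 99.97%. It also puts 99.4% of the posterior on an odds ratio below 0.001 in the first table.

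**3. Same tables under Beta(1,1).** The posterior for 0/20 is Beta(1,21), so P(rate lower in the empty arm) = 1 − E[(1 − p)^21], with p the 60-patient arm's rate.

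- 1/60, p ~ Beta(2,60): 1 − (60×61)/(81×82) = 1 − 0.551 = 45%.
- 3/60, p ~ Beta(4,58): 1 − (58×59×60×61)/(79×80×81×82) = 1 − 0.298 = 70%.

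Fisher's exact p is 1.00 and 0.57.

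**4. Same tables with N(0, 2.5^2) on the contrast only** (intercept SD 1000), by numerical integration: 71.6% and 88.0%. With SD 2.5 on the intercept as well: 79% and 90%.

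| Table | N(0, 1×10^6) | N(0, 2.5^2) on contrast | Beta(1,1) |
|---|---|---|---|
| 0/20 v 1/60 | 99.9% | 72% | 45% |
| 0/20 v 3/60 | 99.97% | 88% | 70% |

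**5. Where the problem is absent.** With filled cells, 10/20 versus 5/20 gives P(higher rate) 95.4% under the wide prior and 94.5% under Beta(1,1); 6/20 versus 5/20 gives 64.3% and 63.3%. With both arms empty (0/20 and 0/20) the wide prior gives 66.7% rather than 50%: not symmetric, but not near-certainty.

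**6. How often an arm of 20 is empty.** 0.95^20 = 36%; 0.90^20 = 12%; at the plan's 25% placebo response rate, 0.75^20 = 0.3%.

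**The case against.** **No affected endpoint is named.** This stands. The outcomes under Study procedures are scale scores (MADRS, YMRS, CGI-BP, UKU). Mood switch is not defined as an outcome, and nothing says that UKU items will be dichotomised or counted. A reader might infer that the plan will declare near-certain benefit or safety on side effects or mood switches. The documents do not support that: they set a prior and a model class for additional analyses without listing the outcomes, and the 5% and 10% rates are assumptions.

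**The decisive analyses are untouched.** This also stands. It would be wrong to infer that the responder comparison or the dropping of arms is distorted; both use Beta(1,1).

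**Twenty per arm may be too few.** Partly right. Study Design re-randomises week-8 non-responders to a treatment not yet received. Applying the plan's three response scenarios to the first 80 patients, exposure per treatment is 20 plus one third of the other arms' non-responders. This runs from 20 + (10+10+6)/3 = 28.7 to 20 + (15+15+15)/3 = 35. At 30 exposed, the chance of an empty arm falls to 0.95^30 = 21% and 0.90^30 = 4%. The plan does not say how these patients would enter such an analysis. Larger arms make the problem rarer but do not remove it.

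**Convergence checks would catch it.** They may flag poor mixing. But the integration above involves no MCMC: the exact posterior has this property, so a well-converged chain would reproduce it.

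**The alternatives disagree with each other.** True: 72% against 45% in the first table. Beta(1,1) adds one event and one non-event to each arm, which moves the smaller arm more (posterior means 1/22 = 4.5% and 2/62 = 3.2%). Neither figure is the right answer. The case for change is that both stay well short of certainty when the data are nearly uninformative.

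**Conclusion.** The point holds within narrow limits and is minor. On the log-odds and log scales, when exactly one compared arm is empty, the stated prior produces 99.9% (0/20 versus 1/60) or 99.97% (0/20 versus 3/60), where Beta(1,1) gives 45% and 70%. It does not touch the primary response analysis, the pruning rule, linear-scale outcomes or tables with events in both arms.

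The figures assume that 1×10^6 is a variance. Read as an SD the effect is stronger; read as a precision it would contradict the plan's own description of a diffuse prior. How often the problem would arise depends on assumed event rates and on outcomes that the plan leaves unspecified.

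One further reading should stay conditional. The screen for baseline confounders uses a 99% posterior threshold for group differences, but the plan does not say which model it applies to proportions. Only if that model is the logistic one could an empty cell pass that half of the screen. A correlation with outcome would still be required, and the consequence would be an extra covariate-adjusted analysis beside the unadjusted one.

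**What to change.** In General Data Analytic Strategies:

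- Keep N(0, 1×10^6) for linear-scale outcomes and for model intercepts, and state that 1×10^6 is a variance.
- For treatment contrasts in logistic and Poisson models, use a weakly informative prior such as N(0, 2.5^2) on the log-odds or log-rate scale.
- For unadjusted binary outcomes, report the Beta(1,1) result as a sensitivity analysis, because the two priors differ in sparse tables.

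The cost is a sentence or two in the plan, one prior setting in the software and a short extra table. The statistical price is mild shrinkage of extreme odds or rate ratios.
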